2 HYPOTHESIS AND OBJECTIVES

2.1 Primary Objectives

To evaluate the potential hypomethylating effects of freeze-dried black raspberries (BRBs) in the peripheral blood of patients with myelodysplastic syndrome or myelodysplastic syndrome/ myeloproliferative neoplasms(MDS/MPN) after three cycles of BRB administration.

2.2 Secondary Objectives

- 1. To evaluate the toxicity of BRBs in patients with MDS or MDS/MPN.
- 2. To evaluate the hematological response according to modified IWG criteria (Appendix 2) in patients with MDS or MDS/MPN regardless of the initial blood count.
- 3. To evaluate the anthocyanin concentrations in peripheral blood of patients prior to and after administration of BRB powder on Cycle 1 Day 1 of treatment.

3 STUDY DESIGN

3.1 General Description

This is a phase II single-group pilot study. This trial is designed to evaluate efficacy and methylation. This study's overarching aim is to evaluate the systemic effects of BRBs in patients with MDS or MDS/MPN. Eighteen patients with MDS or MDS/MPN will be treated with 25 gm (2x/day) of BRB powder taken orally in 8 ounces of water. If the patient is unable to tolerate the taste of the BRB powder mixed in water, he or she may mix it with 8 ounces of milk, ice cream or a smoothie.

Anthocyanins in the blood will be measured within three hours prior to BRB administration, and two hours (+/- 30 minutes) after the first dose. Urine anthocyanins will be measured within three hours prior to BRB administration and three hours (+/-30 minutes) after the first BRB dose. Both of those time points were chosen based on previous studies demonstrating that the maximum concentrations of anthocyanins and ellagic acid in plasma occurred at one to two hours, and maximum quantities in urine appeared from zero to four hours. (20) Methylation status will be measured within three hours prior to BRB administration in cycles 1–4, 7, 10 and at the end of treatment visit.

Patients will receive oral BRBs while receiving their supportive care for a period of at least three cycles. At cycles 4 and 7, day 1, the patient will be assessed for response (Appendix 2) and toxicity. If the patient is tolerating BRBs well and is benefiting from therapy, he or she will continue treatment for a total maximum of 12 cycles. Tolerating well is defined as no grade 3 or 4 toxicity.

*Benefiting from therapy (for cycle 3 disease assessment) defined as CR, PR, HI, stable disease with no disease progression (see Appendix 2).

**Benefiting from therapy (for cycle 6 disease assessment) defined as CR, PR or HI (see Appendix 2).

3.2 Number of Patients

The study team will enroll 18 MDS or MDS/MPN patients.

3.3 Primary Endpoint(s)

To evaluate the potential hypomethylating effects of freeze-dried black raspberries (BRBs) in the peripheral blood of patients with myelodysplastic syndrome or myelodysplastic syndrome/ myeloproliferative neoplasms (MDS/MPN) after three cycles of BRB administration.

3.4 Secondary Endpoint(s)

- 1. To determine the toxicity of BRB by assessing the incidence of adverse events related to BRB.
- The patient's best clinical response will be assessed, based on a modified International Working Group (IWG) response criteria (erythroid, platelet, neutrophil) (Appendix 2) in myelodysplastic syndrome or myelodysplastic syndrome/ myeloproliferative neoplasms (MDS/MPN).
- 3. To evaluate the anthocyanin concentrations in peripheral blood of patients prior to and after administration of BRB powder on Cycle 1 Day 1 of treatment.

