Number of Patients	The study team will enroll 18 patients with MDS or MDS/MPN.					
Subject Participation Duration	After three and six cycles of treatment, if patients are benefiting from the regimen, they continue treatment for a total maximum of 12 cycles.					

Duration of Follow up	Follow-up is required 30 days (+4 days) from treatment discontinuation.				
Estimated Time to Complete Enrollment:	The study will reach accrual approximately 24 months from when the first patient is dosed.				
Safety Assessments	Patients will be seen every cycle by the study staff for compliance and toxicity evaluation. No toxicity is expected from consumption of freeze-dried BRBs powder at a level of 50 grams per day. However, side effects are always a possibility. The NCI Toxicity Criteria version 4.0 will be employed in this study to record any adverse events.				
Efficacy Assessments	Peripheral blood samples will be collected day 1 of cycles 1–4, 7, 10, and end of treatment for evaluation of methylation status of mononuclear cells. Assays will include plasma uptake of berry components, measurement of berry anthocyanins in urine, isolation of peripheral blood monocytes and analysis of DNA methylation.				
Unique Aspects of this Study	This study will test the novel suppressive role of black raspberries.				

1. Refer to appendix 4.

2. BRBs will be dispensed every cycle for a maximum of 12 cycles.

3. If the patient is tolerating BRBs well and is benefiting from therapy after cycles 3 and 6, then, the patient will continue treatment for a total maximum of 12 cycles.

4. A follow-up visit is required 30 days (+4 days) from treatment discontinuation.

8

STUDY CALENDAR

The below study chart is described in detail in Sections 5 and 6.

Study Calendar

Period/Procedure	Screening	g Treatment .			End of Treatment		
Study Day/Visit Day Cycle=28 days	-28 to 0 Days ¹	C1D1	C2 & C3, D1 (+/- 4 days)	C4 & C7, D1 (+/- 4 days)	C10D1 (+/- 4 days)	C5-C6 & C8-C9 & C11-C12, D1 (+/- 4 days) ¹⁰	Follow-up ²
Informed consent	Х						
Demographics	Х						
Inclusion/exclusion criteria	Х						
Medical history/height	Х						
Medication history ⁴	Х						
Drug Administration							
Black raspberries 25 gm (BID) ³		х	х	х	Х	х	
Clinical procedures							
Concomitant medications	Х	Х	Х	Х	Х	Х	Х
Diet assessment ¹⁴		Х	Х	Х	Х	Х	
ECOG Performance Status ¹⁶	Х			Х			Х
Weight		Х		Х			Х
AE assessment ¹¹		Х	х	Х	Х	Х	Х
Physical exam	Х	Х					Х
Laboratory procedures							

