6.2 Dosing Delays/Dose Modifications

Treatment or visit delays for public holidays or weather conditions do not constitute a protocol violation.

See the table below for dose modification requirements for nonhematological toxicities deemed clinically significant and related to BRB treatment by the treating physician.

Dose Modifications			
Dose Level	Dose of Study Drug		
0	25 grams twice a day with each dose separated by at least six hours (mixed in 8 ounces of water) ¹		
1	≥ grade 1 toxicity related to BRB treatment and unable to tolerate then dose reduce to 25 grams QD		
2	≥ grade 2 toxicity or grade 3 allergic reaction related to BRB treatment and/or unable to tolerate, withdraw patient from study		
Footnotes ¹	If unable to tolerate the taste, mix BRB with milk, ice cream or smoothie.		

Toxicity will be assessed according to the NCI Common Terminology Criteria for Adverse Events Version 4.0 (CTCAE v4.0).

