7 ADVERSE EVENTS: DEFINITIONS AND REPORTING REQUIREMENTS

7.1 Defining and reporting an Adverse Event

Definition. Any clinically relevant deterioration in laboratory assessments or other clinical finding is considered an AE.

Prior to the trial. Planned hospital admissions or surgical procedures for an illness or disease that existed before the patient was enrolled in the trial are not to be considered AEs unless the condition deteriorated in an unexpected manner during the trial (e.g. surgery was performed earlier or later than planned).

Reporting source. AEs may be spontaneously reported by the patient and/or in response to an open question from study personnel or revealed by observation, physical examination or other diagnostic procedures.

For non-serious AEs, the investigator must determine both the intensity of the event and the relationship of the event to study drug administration.

Signs or symptoms reported as adverse events will be graded and recorded by the investigator, according to the CTCAE version 4. When possible, signs and symptoms indicating a common underlying pathology should be noted as one comprehensive event.

Follow-up of Adverse Events

All adverse events will be followed with appropriate medical management from the first dose of BRBs until 30 days following the last dose of treatment.

The investigator and his or her team will follow the Medical College of Wisconsin policies related to adverse event reporting.

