Reporting SAEs

Serious AEs must be reported from the first dose of BRBs through 30 days after completion of study treatment or until they are resolved or are clearly determined to be due to a patient's stable or chronic condition or intercurrent illness(es).

For serious AEs, the investigator must determine both the intensity of the event and the relationship of the event to study drug administration.

Since this is an investigator-initiated study, the principal investigator, also referred to as the sponsor-investigator, is responsible for reporting serious adverse events (SAEs) to any regulatory agency and to the sponsor-investigator's IRB when required.

AEs which are serious must be reported to the Data Safety Monitoring Committee (DSMC) from the first dose of BRBs through 30 days after completion of treatment on the study.

Reporting to the Data and Safety Monitoring Committee

Regardless of expectedness or causality, all SAEs must also be reported to the DSMC as soon as possible, but no later than five calendar days of the sponsor-investigator's observation or awareness of the event.

Report Method: The investigator will use email to report SAEs to the DSMC. The SAE report must include event term(s), serious criteria, and the sponsor-investigator's or sub-investigator's determination of both the intensity of the event(s) and the relationship of the event(s) to study drug administration. Intensity for each SAE, including any lab abnormalities, will be determined by using the NCI CTCAE version 4 as a guideline whenever possible.

The criteria are available online at http://ctep.cancer.gov/reporting/ctc.html.

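### Toxicity is measured only by adverse events judged related to BRB, with no any-cause summary planned beside it, so attribution error in either direction passes straight into the result

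*Combined protocol and SAP*

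**What the plan says.** The first secondary objective in Section 2.2 has no causal limit: "To evaluate the toxicity of BRBs in patients with MDS or MDS/MPN". The endpoint that serves it, Section 3.4 item 1, does: "To determine the toxicity of BRB by assessing the incidence of adverse events related to BRB".

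Relatedness is the investigator's call for both classes of event. Section 7.1 states: "For non-serious AEs, the investigator must determine both the intensity of the event and the relationship of the event to study drug administration". Section 7.2 says the same of serious events: "For serious AEs, the investigator must determine both the intensity of the event and the relationship of the event to study drug administration". In Section 6.2 the treating physician makes a further relatedness judgement for dose changes, on toxicities "deemed clinically significant and related to BRB treatment by the treating physician". None of these sections gives causality categories or criteria, and no independent adjudication is described. The only causality tick-box is on the sample pregnancy form in Appendix 7, which concerns pregnancy outcomes.

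On design, Section 3.1 states: "This is a phase II single-group pilot study". On expectation, the Safety Assessments row of the protocol summary states: "No toxicity is expected from consumption of freeze-dried BRBs powder at a level of 50 grams per day". The next sentence of that row allows that side effects may still occur.

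Section 10 covers berry components, methylation, power and a toxicity pause rule. It contains no adverse event analysis.

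**The concern.** With no comparator, attribution is the only thing that separates a BRB effect from the course of the disease and its treatment. Other explanations are always to hand. Patients enter with MDS or MDS/MPN and cytopenias, may be receiving transfusions, growth factors or hydrea, and may have a concurrent active malignancy (Sections 4.1 and 4.2). The potential effects listed in Section 8.1 (headache, dizziness, nausea, vomiting, diarrhea, cramping) are non-specific.

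The endpoint therefore reports the event and the judgement as one number, and a reader cannot separate them. If a true effect is put down to disease or co-medication, the number is too low. If a background symptom is put down to the powder, it is too high. Without an any-cause figure alongside, neither error can be seen. Low toxicity is part of the trial's rationale (Section 1), so this number will be read as a finding.

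**Working it through.** The plan gives no sample size, precision or analysis for toxicity, so there is no toxicity figure to reproduce. The check has two parts.

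**1. Where an event goes, by type**

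| Event | Recorded, graded and assessed for relationship | Reaches the DSMC regardless of cause | In a planned result |
|---|---|---|---|
| Serious, any cause | Yes (7.2) | Yes (7.2) | Only if called related (3.4) |
| Grade 4-5, any cause | Yes (7.1, 7.2) | Yes (11.5) | Only if called related |
| Unexpected grade 3, any cause | Yes (7.1, 7.2) | Yes (11.5) | Only if called related |
| Other non-serious events, including grade 1-2 | Yes (7.1) | Not required | Only if called related |

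The last row is the real gap. It matters because the BRB-related effects reported in the earlier Barrett's esophagus study (Section 1: 3 of 20 patients, with epigastric pain, diarrhea and constipation) were all grade I.

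**2. How far attribution alone can move the endpoint at n = 18**

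Inputs: N = 18 (Section 3.2); all patients count for toxicity from first dose (Section 9.1). Assumption, not from the documents: 6 of the 18 have a given event.

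Formula: exact (Clopper-Pearson) 95% interval for x of n. The lower limit is the 2.5% point of Beta(x, n − x + 1) and the upper limit is the 97.5% point of Beta(x + 1, n − x).

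| Called related, of the 6 | Endpoint as defined | Exact 95% CI | Any-cause figure |
|---|---|---|---|
| 6 | 6/18 = 33.3% | 13.3% to 59.0% | 6/18 |
| 3 | 3/18 = 16.7% | 3.6% to 41.4% | 6/18 |
| 0 | 0/18 = 0% | 0% to 18.5% | 6/18 |

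The same six events can give any endpoint value from 0% to 33.3%, while the any-cause figure stays at 33.3%. The table does not say which row is right. If BRB truly caused three of the six, the first row overstates toxicity and the last understates it. The any-cause figure would then overstate it too.

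The intervals for 3/18 and 6/18 overlap widely, so at this sample size the example shows a shift in the reported message, not a statistically clear difference.

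**The case against.** The strongest reply is that any-cause safety is already covered. CTCAE grading applies to all adverse events, every dosed patient is evaluable, all serious events go to the DSMC whatever the cause, and the DSMC reviews unexpected grade 3 and all grade 4-5 events and can stop the trial. This stands. A reader might infer that events called unrelated vanish, or that safety oversight rests on attribution; the documents do not support either reading. What the reply does not meet is that oversight is not a planned result, and that non-serious lower-grade events fall outside the required DSMC review.

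A second reply is that the direction of error is unknown. This also stands. A reader might infer that the endpoint must understate harm, because the protocol expects no toxicity. But the protocol summary goes on to allow for side effects, Section 10 rules out only severe toxicity as expected, Section 8.1 lists gastrointestinal symptoms to be monitored, and Section 1 reports earlier ones as likely related to BRB. Investigators could as easily over-attribute.

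A third reply is that uncontrolled any-cause rates in cytopenic patients treated for up to 12 cycles would mix in disease and co-medication events. That is correct, and it argues against replacing the related-event endpoint. It does not argue against showing both.

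Finally, a reader might infer that the 15% pause rule is weakened as well. Section 10 does not say whether that rule counts related events only, so this cannot be concluded.

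**Conclusion.** The point holds as a reporting gap. The sole toxicity endpoint is narrower than its objective. It depends on an investigator judgement made without stated criteria, in a trial that is open by design (the documents do not use that word, but it follows from a single group), and no any-cause summary is planned beside it. Error in either direction would pass unseen into the result.

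The size is unknown. The 6/18 and 3/18 figures are an illustration resting on an assumed event count and an assumed split. No stated number in the plan is wrong. This is a secondary endpoint in an 18-patient pilot whose primary endpoint is methylation, so the change is a worthwhile, inexpensive improvement and does not bear on the trial's validity.

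**What to change.** Keep the BRB-related incidence in Section 3.4 item 1. Add to Section 3.4 and Section 10:

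- the proportion of all dosed patients with each treatment-emergent adverse event of any cause (first dose to 30 days after last dose, the window already used in Section 7.1), by worst CTCAE v4.0 grade per patient, with exact 95% confidence intervals;
- the BRB-related figures in adjacent columns of the same table;
- separate blocks for haematological and non-haematological events;
- a sentence saying that any-cause rates include disease and co-medication events, so neither figure alone estimates BRB toxicity.

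Event, grade and relationship are already collected, so no new data or visits are needed and N stays 18. The cost is a few sentences and one extra table. The drawback is that the any-cause rates will look higher, which the added sentence addresses.

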3.5 Study Timeline

Patients may continue BRB treatment for a maximum of 12 cycles from the time of study entry.

3.6 Study Completion

The study will reach accrual approximately 24 months from when the first patient is dosed.

4 PATIENT SELECTION

Eligibility Criteria

The written informed consent must be obtained from the patient prior to enrollment and any study-specific procedures. Patients must have baseline evaluations performed prior to enrollment and the first study drug dose. The following criteria apply to all patients enrolled onto the study unless otherwise specified.

4.1 Inclusion Criteria

A potential subject must meet all the following inclusion criteria to be eligible to participate in the study.

1. Patients must have a confirmed diagnosis of myelodysplastic syndrome or myelodysplastic syndrome/ myeloproliferative neoplasms (MDS/MPN) proven by bone marrow biopsy/aspirate.

- 2. Patients with cytopenias (blood cell counts lower than the institutional lower limit of normal within the eight weeks prior to the study) who are receiving or received:
 - red blood cell transfusions
 - observation
 - platelet transfusions
 - erythropoietin
 - granulocyte colony-stimulating factors
 - granulocyte-macrophage colony-stimulating factors
 - hydrea
- 3. Age >18 years.
- 4. Predicted life expectancy of at least 12 weeks.
- 5. Patients should be expected to stay on the same therapy for the period of the study.
- 6. Patients who do not have an indication for and/or are believed to be unable to tolerate a hypomethylating agent are eligible for the study.
- 7. Reproductive requirements:

Female patients must meet one of the following:

- Postmenopausal for at least one year before the screening visit, or
- Surgically sterile, or
- If they are of childbearing potential, agree to practice two effective methods of contraception from the time of signing of the informed consent form through 30 days after the last dose of study drug, AND
- Must also adhere to the guidelines of any treatment-specific pregnancy prevention program, if applicable, or
- Agree to practice true abstinence when this is in line with the preferred and usual lifestyle of the subject. (Periodic abstinence [e.g., calendar, ovulation, symptothermal, postovulation methods] and withdrawal are not acceptable contraception methods.)

Male patients, even if surgically sterilized (i.e., status postvasectomy), must agree to one of the following:

- Practice effective barrier contraception during the entire study treatment period and through 30 days after the last study drug dose, OR
- Must also adhere to the guidelines of any treatment-specific pregnancy prevention program, if applicable, OR
- Agree to practice true abstinence when this is in line with the preferred and usual lifestyle of the subject. (Periodic abstinence [e.g., calendar, ovulation, symptothermal, postovulation methods] and withdrawal are not acceptable methods of contraception.)
- 8. Ability to understand a written informed consent document, and the willingness to signit.

4.2 Exclusion Criteria

A potential subject who meets any of the following exclusion criteria is ineligible to participate in the study.

- 1. Previously received hypomethylating agents.
- 2. Allergy to black raspberries.
- 3. Inability to swallow oral medication.

- 4. Inability or unwillingness to comply with the BRB administration requirements.
- 5. Uncontrolled intercurrent illness, including, but not limited to, symptomatic congestive heart failure, or psychiatric illness/social situations, that, in the treating investigator's discretion, would limit compliance with study requirements. Concurrent active malignancy is not an exclusion criterion.
- 6. Active infection not well controlled by antibacterial or antiviral therapy.
- 7. Pregnant or lactating women.
- 8. Participation in clinical trials with other investigational agents not included in this trial, within 14 days of the start of this trial and throughout the duration of this trial.
- 9. Patients with allergies to other members of the Rosacea family, including but not limited to apple, almond, apricot, cloudberry, blackberry, etc.

5 STUDY ENTRY AND WITHDRAWAL; STUDY PROCEDURES

5.1 Screening Tests and Procedures

The study-specific assessments are detailed in this section and outlined in the Study Calendar. Screening assessments, unless otherwise specified, must be performed within 28 days prior to the day 1 visit. All on-study visit procedures are allowed a window of ± 4 days unless otherwise noted. Treatment or visit delays for public holidays or weather conditions do not constitute a protocol violation.

A written, signed informed consent form (ICF) and a Health Insurance Portability and Accountability Act (HIPAA) authorization must be obtained before any study-specific assessments are initiated.

All patients who are consented will be registered in OnCore[®], the MCW Cancer Center Clinical Trial Management System. The system is password protected and meets HIPAA requirements. Once a patient has been consented, they will be assigned a screening ID by the clinical research coordinator that will be used to identify them throughout the study. The patient identifier will start with BRB and then chronologically numbered there after (BRB-001, BRB-002, BRB-003, etc.).

5.2 Enrollment Process

A subject will be considered enrolled onto the study once they have signed consent, have successfully met all screening criteria, the eligibility criteria has been reviewed and accepted by the PI or a sub-investigator, and entered into OnCore. Contact [name] with any eligibility questions at [contact].

5.3 Pretreatment Period

The screening procedures and assessments must be completed within 28 days of the Day 1 visit unless otherwise specified in the study parameter schedule.

Refer to the study calendar for specifics:

- Informed consent
- Demographics

- Inclusion/exclusion criteria
- Medical history
- Medication history
- Concomitant medications
- ECOG performance status
- Height
- Physical examination
- Complete blood count (CBC) with differential and platelet count
- Serum or urine pregnancy test (for women of childbearing potential)
- Serum chemistry panel, including: Alkaline phosphatase, aspartate aminotransferase/alanine aminotransferase (ALT/AST), total bilirubin, blood urea nitrogen (BUN), creatinine, total protein, albumin, potassium, sodium, chloride, bicarbonate, glucose.

